10.3. Enrollment Control

A minimum of 98 enrolled subjects are needed to adequately assess the primary endpoint at 6 months after initial treatment. To account for attrition, minimum enrolment shall be 109 subjects, assuming a maximum attrition of 10% for all reasons at 6 months. The enrollment cap for each study site is 25% of total enrolled subjects, which is 27 subjects. The study recruitment will stop when 109 qualified subjects completed enrollment.

11. Study Methods

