11.10. Study Completion

All subjects who completed the 12 months follow-up, or withdrawn (due to death or loss to follow-up), or will be treated as study termination. Any adverse events occurred afterwards will be addressed by the physician per standard treatment.

Subjects may withdraw their consent and discontinue participation in the clinical study at any time, for any reason, without prejudice to further treatment. If a subject no longer wants to receive study treatment, but is willing to come for follow-up appointments, the subject's request should be honored, if possible.

If for any reason a subject is withdrawn or terminated before completing the study, the reasons for withdrawal or termination must be documented.

If a subject discontinues treatment due to an adverse event or clinical laboratory abnormality, the subject should be followed-up until the event resolves or the subject stabilized.

12. Statistical Considerations

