12.1. Endpoints

12.1.1. Primary Endpoint

The primary endpoint of the study is 6-month ORR. Objective tumor response will be assessed by The European Association for the Study of the Liver (EASL) Response Evaluation Criteria in Solid Tumors and a modified Response Evaluation Criteria in Solid Tumors (mRECIST¹⁹). The mRECIST criteria can be more accurate to predict long-term survival in HCC subjects treated with chemoembolization²⁰. The subject achieves complete response (CR) or partial response (PR) will be regarded as a responder. A subject without tumor assessment after the initiation of the treatment will be regarded as a missing data.

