12.1.1.1. Hypotheses

The primary hypotheses is the 6-month ORR in subjects treated with transcatheter arterial chemoembolization with drug-loaded Tandem Microspheres exceeds the PG under a one-sided significance level of 2.5%. The PG development is based on PRECISION V, an international multicenter study. The ORR will be assessed based on the EASL criteria.

The null (H_0) and the alternative (H_1) hypotheses for the primary effectiveness endpoint are as follows:

 H_0 : $P_e \le PG$ (not met)

 $H_1: P_e > PG \text{ (met)}$

where P_e is the expected 6-month ORR (%).

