12.1.1.2. Sample Size

The overall sample size is driven by the primary effectiveness endpoint. Approximately 109 subjects are planned to be enrolled in the study. The sample size justification is based on the following assumptions.

- Power $\geq 85\%$
- One-sided significance level = 2.5% (alpha)
- PG for 6-month ORR = 45%
- Expected 6-month ORR = 60%
- A minimum of 98 evaluable subjects are required for 6-month assessment
- Attrition rate = 10% (loss to follow-up in 6 months)
- A sample size of 109 subjects will be enrolled in the study

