13.3. Core Laboratory

The STOPPER China clinical trial will use a Core Laboratory to conduct independent data analysis. See the Manuel of Operations for operating guide on data collection, analysis and interpretation.

The independent Core Laboratory will assess the tumor response using EASL and mRECIST criteria (at baseline, 30-day, 3-month, 6-month and 12-month post initial treatment) based on the plain scan and enhanced MRI imaging performed for subjects enrolled at respective study sites.

14. Protocol Amendments

If a protocol revision is necessary which affects the rights, safety or welfare of the subjects or scientific integrity of the data, an amendment is required. Appropriate approvals (e.g., IEC/CFDA) of the revised protocol must be obtained prior to implementation.

15. Protocol Deviations

An Investigator must not make any changes or deviate from this protocol, except to protect the life and physical well-being of a subject in an emergency. An investigator shall notify the Sponsor and the reviewing IEC of any deviation from the investigational plan to protect the life or physical well-being of a subject in an emergency, and those deviations which affect the scientific integrity of the clinical investigation. Such notice shall be given as soon as possible, but no later than 5 working days after the emergency occurred, or per prevailing local requirements, if sooner than 5 working days.

All deviations from the investigational plan, with the reason for the deviation and the date of occurrence, must be documented and reported to the Sponsor using the EDC CRF. Centers may also be required to report deviations to the IEC, per local guidelines and government regulations.

All protocol deviations (PDs) are classified as "major" or "minor" as defined below:

- A major PD is a protocol deviation that directly or potentially disrupts the study progress (i.e., the study design, study data and results can be compromised), OR a protocol deviation that compromises the safety and welfare of study participants.
- A minor PD is a protocol deviation that does not disrupt study progress (i.e., the study design, study data and results will not be compromised), AND does not compromise the safety and welfare of study participants.

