3.1.1 Definition of the ORR

Objective tumor response will be assessed by two response evaluation systems for solid tumors:

- European Association for the Study of the Liver (EASL); and
- Modified Response Evaluation Criteria in Solid Tumors (mRECIST).

The EASL and mRECIST responses measure on MRI in HCC subjects treated with chemoembolization to predict long-term survival. The mRECIST response demonstrated higher survival correlation than the EASL (cf. Prajapati et al, 2013 Annuals of Oncology).

EASL Response Assessment of Target Lesion for HCC:

Response Category	EASL Criteria
Complete Response (CR)	Disappearance of all known disease and no new lesions determined by two observations not less than 4 weeks apart
Partial Response (PR)	At least 50% reduction in total tumor load of all measurable lesions determined by two observations not less than 4 weeks apart
Stable Disease (SD)	Any cases that do not qualify for either PR or PD
Disease Progression (PD)	At least 25% increase in size of one or more measurable lesions or the appearance of new lesions

mRECIST Response Assessment of Target Lesion for HCC:

Response Category	mRECIST Criteria
Complete Response (CR)	Disappearance of any intratumoral arterial enhancement in all target lesions
Partial Response (PR)	At least a 30% decrease in the sum of the diameters of viable (enhancement in the arterial phase) target lesions, taking as reference the baseline sum of the diameters of target lesions.
Stable Disease (SD)	Any cases that do not qualify for either PR or PD
Disease Progression (PD)	An increase of at least 20% in the sum of the diameters of viable (enhancing) target lesions, taking as a reference the smallest sum of the diameters of viable (enhancing) target lesions recorded since treatment started.

A responder is for a subject being assessed as CR or PR as opposed to a non-responder is for being assessed as SD or PD (i.e. numerator). Subjects with valid assessment (i.e. CR, PR, SD, or PD) will be considered as evaluable subjects (i.e. denominator).

A subject without 6 month tumor assessment after the treatment initiation (i.e. the 1st DEB-TACE) will be regarded as a missing data and will be excluded from the primary effectiveness endpoint analysis.

3.1.2 Effectiveness Hypotheses

The primary effectiveness hypothesis to be tested is that the 6-month ORR in subjects treated with Tandem meets the PG at a one-sided significance level of 2.5%.

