The null hypothesis (H_0) states that the PG is not met as opposed to the alternative hypothesis (H_1) which states that the PG is met. The hypotheses inequalities are shown below:

 H_0 : $Pt \le PG$ (not met)

 H_1 : Pt > PG (met)

where Pt is the 6-month ORR for the subjects treated with Tandem and the PG is 45%. The PG development is based on the PRECISION V, an international multicenter phase II randomized clinical trial (RCT).

3.1.3 Effectiveness Sample Size

The overall sample size is driven by the primary effectiveness endpoint. Approximately 109 subjects are planned to be enrolled in the single-arm study. The sample size justification is based on the following assumptions.

- Power > 85%
- One-sided significance level (alpha) = 2.5%
- PG for 6-month ORR = 45%

- Expected 6-month ORR = 60%
- A minimum of 98 evaluable subjects to be required at 6 months
- Attrition rate in 6 months $\leq 10\%$
- A maximum of 109 subjects to be enrolled in the study at baseline

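### SAP 3.1.1 drops treated subjects who die before the 6-month scan from the primary ORR; deaths should count as non-responders, and the SAP and Protocol should share one definition of missing

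*SAP*

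**What the plan says.** SAP 3.1.1 takes as denominator the subjects with a valid response category. A subject without a 6-month assessment after the first treatment "will be regarded as a missing data and will be excluded from the primary effectiveness endpoint analysis". Death and progression on an earlier scan are not mentioned as exceptions.

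SAP 3.1.2 defines the tested quantity on a wider group: "where Pt is the 6-month ORR for the subjects treated with Tandem and the PG is 45" per cent.

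Protocol 12.1.1 is worded differently: "A subject without tumor assessment after the initiation of the treatment will be regarded as a missing data". It names no visit and does not say that such subjects leave the analysis. Protocol 12.1.1.1 fixes the criterion for the hypothesis: "The ORR will be assessed based on the EASL criteria".

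Two further places show which subjects the SAP rule reaches. Protocol 11.10 lists death among the ways of leaving the study: "or withdrawn (due to death or loss to follow-up), or will be treated as study termination". Protocol 13.3 says that the core laboratory "will assess the tumor response using EASL and mRECIST criteria (at baseline, 30-day, 3-month, 6-month and 12-month post initial treatment", so progression at 30 days or 3 months can be on record before a 6-month scan is missed.

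The sizing allows for losses. Protocol 10.3 enrols 109, "assuming a maximum attrition of 10% for all reasons at 6 months", and Protocol 12.1.1.2 states: "A minimum of 98 evaluable subjects are required for 6-month assessment".

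**The concern.** A subject who has died before 6 months has a known result for a 6-month response endpoint: there is none. Removing that subject from numerator and denominator gives the death, in effect, the average response rate of those who were scanned. If excluded subjects respond less often than scanned ones, the observed ORR is biased upward. There is no control arm in which a similar bias could offset this. The rule also sets the denominator of the trial's only hypothesis test.

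The wording conflict adds to this. A subject with a 3-month scan and no 6-month scan is missing under the SAP, but not on the plain words of Protocol 12.1.1. Two analysts could reach different denominators from the same data.

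**Working it through.** **Inputs.** Goal 45%, expected ORR 60%, one-sided alpha 2.5%, power 85%, 98 evaluable, 109 enrolled (SAP 3.1.3); normal-approximation test (SAP 3.1.4); attrition up to 10% for all reasons (Protocol 10.3), so 109 − 98 = 11 missing. Success means a 97.5% lower bound above 45% (SAP synopsis; Protocol 12.1.1.4).

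**1. The plan's own figures.**
- n = [(1.960·√(0.45·0.55) + 1.036·√(0.60·0.40)) / 0.15]² = 97.7, rounded up to 98; 98/0.90 = 108.9, rounded up to 109. Both reproduce.
- The output in SAP 7.2 for 54/98 reproduces: z = (0.5510 − 0.45)/√(0.45·0.55/98) = 2.010, one-sided p = 0.022, Wald lower bound 45.25%.
- 53/98 gives z = 1.807, p = 0.035, so the pass mark at 98 is 54. SAP 3.1.5 says 52, but 52/98 gives z = 1.604, p = 0.054 and fails. That is a separate slip; 54 is used here.
- The score test and the Wald bound give the same pass marks: 54 at n = 97 and 98, 55 at 99 and 100, 56 at 101 and 102, 57 at 103, 60 at 109.

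**2. Effect on a given result.**
- 54/98 passes. With one dropped subject counted as a non-responder, 54/99 gives z = 1.909, p = 0.028, lower bound 44.74%, and fails.
- Non-responders that must be added to reverse a pass: 1 at 54/98, 3 at 55/98, 5 at 56/98, 7 at 57/98, 9 at 58/98, 11 at 59/98. From 60/98 upward all 11 losses leave a pass (60/109: z = 2.108, p = 0.018).

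**3. False success.** Assume a true ORR of 45% among all 109 treated and 11 missing. Of these, d died or progressed (non-responders) and the rest respond like scanned subjects. The rate among scanned subjects is then r = 0.45·109/(109 − d).
- SAP rule: P[Bin(98, r) ≥ 54].
- Counting the d as non-responders: P[Bin(98, r) ≥ pass mark at 98 + d].
- Example, d = 3: r = 49.05/106 = 0.4627; the pass marks are 54 and 56; the probabilities are 0.0495 and 0.0200.

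| d | r | SAP rule | d counted |
|---|---|---|---|
| 0 | 0.4500 | 2.8% | 2.8% |
| 1 | 0.4542 | 3.4% | 2.2% |
| 2 | 0.4584 | 4.1% | 2.6% |
| 3 | 0.4627 | 5.0% | 2.0% |
| 4 | 0.4671 | 5.9% | 2.5% |
| 5 | 0.4716 | 7.1% | 1.9% |

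The 2.8% at d = 0 comes from the normal approximation, not from missing data. The last column moves up and down because the pass mark is an integer.

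**4. Varying the assumptions.**
- With 5 missing in place of 11: 3.4% against 2.2% (d = 1), 5.0% against 2.1% (d = 3), 7.2% against 2.0% (d = 5).
- With 11 missing, d = 3 and the other 8 responding at rate q, r = (49.05 − 8q)/98: 8.3% against 3.7% for q = 30%, and 3.1% against 1.1% for q = 60%.

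**5. Power with 11 missing.**
- If 60% holds among the 98 scanned, power is P[Bin(98, 0.60) ≥ pass mark at 98 + d]: 86% at d = 0, 81% at d = 1 or 2, 75% at d = 3.
- If 60% holds among all treated, r = 65.4/(109 − d), and power lies between about 84% and 91% for d from 1 to 11 (84.2% at d = 1, 84.9% at d = 3).

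**The case against.** **The design already declares this.** Protocol 12.2.1 specifies per-protocol and as-treated analysis, SAP 4.1 per-protocol, and the trial is sized on 98 evaluable of 109. Neither document says that missing subjects stay in the denominator, so a reader who infers that the SAP breaks a stated Protocol rule goes too far. Protocol 12.1.1 can even be read as meaning the 6-month assessment, since it sits under that endpoint. What stands is a difference in wording and a gap between the target in SAP 3.1.2 and the subjects analysed. Planning for losses fixes their number; it does not make a death uninformative.

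**Sensitivity analyses exist.** Protocol 12.3.3 and SAP 5.5 plan a worst case and a tipping point over all combinations, which already contains the case of every missing subject as a non-responder (54/109, p = 0.17). It would be wrong to say that the plan ignores missing outcomes. But neither analysis enters the success criterion in SAP 3.3, the SAP labels the tipping point post hoc, and the Protocol places it on an ITT set that 12.2.1 does not define.

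**One death does not generally overturn the result.** A reader might infer this from 54/98 and 54/99. It depends on where the integer pass mark steps: 54/97 and 54/98 both pass, as do 55/99 and 55/100. At the expected rate (59/98) all 11 losses must be non-responders.

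**The number affected is unknown.** If all 11 losses were deaths or progressions, false success under the SAP rule would be 18.4%, but nothing in the documents supports that case. Protocol Table 19.1-1 lists death at 0 to 2.4% (0.024·109 = 2.6 subjects), as a complication rate and not 6-month mortality.

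**Progression differs from death.** Repeat treatment is allowed (Protocol 8.2), so a subject who progresses early may still respond by 6 months, and one who progresses but has a 6-month scan stays in the analysis anyway. Scoring early progression with a missing scan as non-response is a convention. It is also one-sided, since an early responder who misses the scan stays missing. This objection stands; the case for deaths does not depend on it.

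**The goal may be on another scale.** SAP 3.1.6 shows its source figure as LOCF in an MITT population, with 93 + 108 = 201 subjects, of 212 enrolled according to Protocol 8.3. The size of any difference cannot be worked out from the documents, and it does not favour exclusion of deaths.

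**Conclusion.** The point holds for deaths: followed as written, SAP 3.1.1 discards a known non-response from the only hypothesis test. For early progression with a missing scan it holds as a matter of stating a convention. With one to five such subjects among 11 missing, false success is 3.4% to 7.1% under the SAP rule and 1.9% to 2.6% when they are counted. This rests on a true all-treated ORR of 45% and on the other missing subjects responding like scanned ones. With no such subjects the two rules agree. Any change of decision is confined to results from 54/98 to 59/98 under the planned attrition. The documents do not support a claim that the result is generally fragile or that the bias is certain to be large. This should be fixed before the primary analysis.

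**What to change.** - **SAP 3.1.1:** count a treated subject who dies before the 6-month assessment as a non-responder in the primary denominator. Apply the same rule, labelled as a convention, to core-laboratory EASL progression followed by a missing 6-month scan. Keep other subjects without a 6-month scan as missing.
- **Protocol 12.1.1:** adopt the same definition of missing.
- **SAP 5.5:** remove the post-hoc label. Pre-specify, on all treated subjects, the worst case (every missing subject a non-responder) and the tipping-point analysis. Report the ORR among subjects with a 6-month scan as supportive.
- **SAP 3.1.3:** state whether the 60% refers to all treated or to scanned subjects.

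The cost is an SAP amendment, a Protocol clarification and some programming on data already collected. The observed ORR may fall. Power may fall too, to 81% with one or two such subjects and 75% with three if the 60% was meant for scanned subjects; if it was meant for all treated, power stays at about 84% to 91%. N need not change.

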3.1.4 Effectiveness Statistical Methods

A normal approximation test (e.g. Chi-Square Test) for comparing the observed 6-month ORR with the PG will be used to assess the effectiveness hypotheses for a minimum of 98 evaluable subjects.

3.1.5 Worst Case Assessment for Effectiveness

The worst case below reflects the analysis for 98 evaluable subjects. If the actual attrition is better than expected, the worst case scenario will be reassessed.

The PG of 45% will require a minimum of 52 responders at 6 months out of 98 evaluable subjects treated with Tandem. That is, the observed 6-month ORR in Tandem will need to be at least 53.1% (52/98) in order to claim the study effectiveness.

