7.2 SAS Codes for Chi-Square Test

The confidence intervals and the Chi-Square test p-value can be produced by the following SAS code.

```
proc freq data=;
  tables xx/binomial(p=) alpha=;
```

run;

For example, the worst case scenario in the PG testing of the primary effectiveness hypotheses is used for the exercise. A dummy frequency table is coded as below.

```
%let total=98; %let yes=54; %let no=&total.-&yes.; data dsn1; yn=1; wgt=&yes.; output; yn=0; wgt=&no.; output; run;
```

A list of SAS codes for Binomial and Chi-Square method is used for PG=45% and 95% confidence limits to control the Type I error under one-sided 2.5% (i.e. two-sided 5%).

```
proc freq data=dsn1 order=data;
  tables yn/ binomial(p=.45) alpha=.05;
  weight wgt;
run;
```

The SAS output for the worst case scenario is presented below.

Binomial Proportion yn = 1

```
Proportion
                           0.5510
ASE
                           0.0502
95% Lower Conf Limit
                           0.4525
95% Upper Conf Limit
                           0.6495
Exact Conf Limits
95% Lower Conf Limit
                           0.4472
95% Upper Conf Limit
                          0.6517
 Test of HO: Proportion = 0.45
ASE under HO
                           0.0503
                           2.0102
One-sided Pr > Z
                           0.0222
Two-sided Pr > |Z|
                           0.0444
        Sample Size = 98
```

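### SAP 3.1.5 sets the success threshold at 52/98 responders, but the planned one-sided 2.5% test first passes at 54/98, the count used in SAP 7.2

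*SAP*

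**What the plan says.** SAP 3.1.5 turns the primary test into a responder count for 98 evaluable subjects: "The PG of 45% will require a minimum of 52 responders at 6 months out of 98 evaluable subjects treated with Tandem". It adds that the observed rate "will need to be at least 53.1% (52/98) in order to claim the study effectiveness". The count is to be reassessed if attrition is better than expected.

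The test behind that count is in SAP 3.1.4: "A normal approximation test (e.g. Chi-Square Test) for comparing the observed 6-month ORR with the PG". SAP 3.1.3 gives the design values: one-sided alpha 2.5%, PG 45%, expected ORR 60%, and "A minimum of 98 evaluable subjects to be required at 6 months". Protocol 12.1.1.4 and the SAP synopsis define success as a one-sided 97.5% lower confidence bound above the PG.

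SAP 7.2 works an example that it describes as the worst case for the primary PG test. The code there sets "let total=98; %let yes=54". The printed output is a proportion of 0.5510, Z = 2.0102, one-sided p = 0.0222, an asymptotic lower limit of 0.4525 and an exact lower limit of 0.4472.

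**The concern.** Sections 3.1.5 and 7.2 of the SAP describe the same worst case, with the same 98 subjects and the same 45% goal, yet one uses 52 responders and the other 54. Both cannot be the minimum. A pass mark is a single integer, so no rounding tolerance covers a difference of two.

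The number matters because SAP section 2 makes the primary effectiveness hypothesis the only statistical hypothesis and the sole basis for study success. Section 3.1.5 is worded as what is needed to claim effectiveness. If the trial ended with 52 or 53 responders of 98, the SAP would contain one pre-specified statement under which it succeeded and one under which it failed. Treating 52 as the rule would also raise the false-positive rate well above the stated level.

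**Working it through.** **Inputs.** PG p0 = 0.45, expected rate p1 = 0.60, one-sided alpha = 0.025 (critical value 1.96), n = 98 evaluable (all SAP 3.1.3). Test: one-sample normal approximation (SAP 3.1.4). Success: 97.5% lower bound above 45% (protocol 12.1.1.4, SAP synopsis).

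**Step 1: reproduce the design.**

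n = [1.96·√(0.45·0.55) + 1.036·√(0.60·0.40)]² / (0.60 − 0.45)² = 97.7, rounded up to 98. Normal-approximation power at n = 98 is 85.1%, and 98/0.9 = 108.9, rounded up to 109. The plan's sample size is correct, so the inputs are being read as intended.

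**Step 2: reproduce SAP 7.2.**

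With x = 54, z = (54/98 − 0.45)/√(0.45·0.55/98) = 0.1010/0.05025 = 2.0102, and one-sided p = 0.0222. The Wald lower limit is 0.5510 − 1.96·0.0502 = 0.4525, and the Clopper-Pearson lower limit is 0.4472. All agree with the printed output.

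**Step 3: apply the same test to neighbouring counts.** The last two columns are exact binomial probabilities of x or more responders of 98.

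| Responders /98 | ORR | z | One-sided p | Wald 97.5% lower bound | Planned test | Type I error if this is the cut-off (true ORR 45%) | Power if this is the cut-off (true ORR 60%) |
|---|---|---|---|---|---|---|---|
| 52 | 53.1% | 1.604 | 0.0543 | 43.2% | fails | 6.7% | 93.3% |
| 53 | 54.1% | 1.807 | 0.0354 | 44.2% | fails | 4.4% | 90.2% |
| 54 | 55.1% | 2.010 | 0.0222 | 45.25% | passes | 2.85% | 86.3% |
| 55 | 56.1% | 2.213 | 0.0134 | 46.3% | passes | 1.8% | 81.3% |

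As a direct check, the test needs x > 98·(0.45 + 1.96·0.05025) = 53.75, so the minimum is 54.

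**Step 4: look for a method that gives 52.** At n = 98 and PG = 45%:

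- score, Wald and Wilson versions: 54
- continuity-corrected test (p = 0.0282 at 54) and exact binomial or Clopper-Pearson (p = 0.0285, lower limit 44.7% at 54): 55
- one-sided 5% instead of 2.5%: 53

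None of these returns 52.

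**Step 5: cut-offs if more than 98 are evaluable**, by the planned test:

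| Evaluable | Minimum responders | ORR | z | Wald lower bound |
|---|---|---|---|---|
| 101 | 56 | 55.4% | 2.110 | 45.75% |
| 104 | 57 | 54.8% | 2.011 | 45.2% |
| 109 | 60 | 55.0% | 2.108 | 45.7% |

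**The case against.** The best defence is that the count in 3.1.5 is only derived. The test, alpha, goal, sample size and power are all specified correctly elsewhere, and the code in 7.2 would return a non-significant p at 52 or 53. On that view the formal test governs and the type I error never rises. This stands in part: the 6.7% applies only if someone uses the stated count in place of the test. But 3.1.5 is written as a requirement for claiming effectiveness, and nothing in the SAP ranks it below the test. Nor is SAP 3.3 a clean backstop, because it compares the lower bound with zero instead of the PG. That is a separate error, but it means the SAP's own success-criteria section does not overrule 52.

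Three narrower points are fair:

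- SAP 7.2 prints only the 54 case. It shows that 54 passes and labels it the worst case; the failure of 52 and 53 comes from the recalculation above.
- Setting 6.7% against the nominal 2.5% (about 2.7 times) mixes an exact error rate with a normal-approximation level. On the exact scale the ratio is 6.7/2.85, about 2.3. On the test's own scale it is 5.4/2.5, about 2.2. Either way the level is more than doubled.
- The plan names a normal-approximation test, so the exact limit printed in 7.2 is not a true rival. Still, the success criterion names no interval method, and at exactly 54/98 the two printed limits fall on opposite sides of 45%. One clarifying sentence is justified.

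**Conclusion.** The threshold in SAP 3.1.5 is wrong as written. With 98 evaluable subjects, a 45% goal and the planned one-sided 2.5% normal-approximation test, the minimum is 54 responders (55.1%), two more than stated. Counts of 52 and 53 satisfy section 3.1.5 and fail the test in 3.1.4. Used as a decision rule, 52 would carry an exact type I error of 6.7% at a true ORR of 45%; 54 carries 2.85%.

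The conclusion assumes that the normal-approximation bound decides and that exactly 98 subjects are evaluable. The sample size of 98 (109 enrolled) and the 85% power claim are unaffected. Because this is the stated pass mark for the trial's only hypothesis, it must be corrected before the primary analysis.

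**What to change.** - In SAP 3.1.5, replace 52 responders and 53.1% (52/98) with 54 responders and 55.1% (54/98), so that it agrees with SAP 7.2.
- State, in 3.1.5 or with the success criterion, that the normal-approximation (asymptotic) 97.5% lower limit from PROC FREQ is the deciding limit and that the exact limit is supportive only.
- Add the cut-offs for better attrition by the same test, for example 56/101, 57/104 and 60/109, and say that the cut-off for any other evaluable number is computed the same way.
- If the sponsor prefers the exact limit, the cut-off becomes 55/98, and the exact power at 60% falls to 81.3%, below the stated 85%. That choice would have to be made and the power restated now.

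The cost is a text correction through the SAP amendment route in section 5.12, made before the primary analysis. The stated pass mark becomes two responders stricter; the planned test does not change.
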